2.2 Trial Design

This is a prospective observational study with no change in clinical practice.

2.3 Trial Statistics

ECG data will be downloaded from the holter device and analysis in holter device software package which derive HRV data. RR interval data from the Isansys patch will be downloaded onto an Excel spreadsheet. The RR interval will be uploaded to Matlab. The Medical Engineering and Clinical Physics department have developed a program in the Matlab environment for analysis and output of HRV data. ECG data will undergo preprocessing to remove artefacts and ectopic beats and be analysed using the Ornstein-Uhlenbeck third-order Gaussian process applied to the heart rate/RR interval.¹¹ This technique has been developed by the Medical Engineering and Clinical Physics department. Once the ECG has been preprocessed heart rate variability will be derived according to the European Society of Cardiology guidelines.²

We will use time domain measures, frequency domain measures and non-linear measures such as the poincare plot, approximate and sample entropy and detrended fluctuation analysis in our analysis of HRV.

Comparison between devices will be assessed by Bland-Altman methodology. The difference between measures recorded from the Holter monitor and the Isansys wireless monitor will be plotted against the average value for each HRV measure for individual patients. Any measure of relationship between the measurement error and the estimate of the true value (average of the two measurements) can be examined. If the difference between the Isansys monitor and the holter monitor is sufficiently small not to cause problems in the clinical interpretation (within 95% limits of agreement), then the Isansys wireless device can be considered to be interchangeable with the gold-standard holter monitoring device.

Heart rate variability data will be analysed statistically as described. Descriptive statistics showing means \pm standard deviation (SD) for continuously distributed variables, and number and proportions for categorical variables will be used for all comparisons. Chi-square tests will be used for categorical outcomes unless assumptions of the test are found to have been violated, in which case Fisher's exact test will be used.

Parametric and nonparametric methods, as determined by the distribution of each variable, will be used to test statistical significance of continuous variables. Logistic regression will be utilized to assess the predictive value of HRV for different outcomes (mortality, ventilator free-days, length of stay, SOFA score) adjusting for covariates.

3. Sample Size, Selection and Withdrawal of Subjects

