irrespective of what measurement technique is employed. The duration of measurement for analysis should also be taken into account. Dependent upon analysis technique the duration of measurement can range from 2 minutes to 24 hours. There remains significant debate as to the optimal duration of measurement, but in general terms this should be suitable for the technique and explained fully in studies.^{10,2} Despite the number of studies using HRV in critical care there remains significant heterogeneity in methodology.³ This uncertainty has led to the need to clarify the factors that can impact upon HRV recording and analysis in the critically ill population. Karmali et al highlight the need for consensus guidelines relevant to critical care medicine.³ The present study hopes to address these issues and compare the robustness of HRV measures obtained from two separate devices under consideration for use in further research at the Royal Liverpool University Hospital.

The devices to be used in this study will be:

1. The Isansys Lifetouch cardiac monitor is a wireless CE marked device produced by Isansys Lifecare Limited. The Isansys lifetouch cardiac monitor continuously records filtered ECG sampled at 1000Hz. ECG data is transmitted and stored in a wireless interface called the Patient Gateway and Lifeguard Server.
2. A Holter monitoring device that is CE marked and validated for medical grade continuous ECG recording. Holter monitoring is considered the gold-standard monitoring for ECG signal analysis. The Holter device will consist of a 12 lead ECG that will record continuously for 72 hours. ECG data will be recorded to a memory card and the ECG data analysed using standard software. The signal will be sampled at 1000Hz.

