2.1 Trial objectives

The **primary objective** is:

- To describe the robustness of data on HRV data obtained by two different monitoring systems in daily care of critically ill patients. The Isansys wireless monitoring device will be compared to the gold-standard holter monitoring device for ECG analysis.

The **secondary objectives** are:

- To identify the most suitable and cost-efficient device for HRV monitoring in critically ill patients.
- To define amendments in data capture and analysis required to proceed to a larger clinical trial
- To generate preliminary data on the variation of HRV in a critical care patients.

Primary outcome:

- Number of interpretable monitoring epochs in each HRV monitoring system after elimination of artefacts, extra beats and interference

Secondary outcomes:

- Correlation and comparison of HRV time, frequency and non-linear measures between the Isansys monitoring device and the gold-standard holter monitoring system.
- Correlation between HRV and onset of arrhythmias (ventricular or atrial)
- Correlation between HRV and cardiorespiratory events that commonly occur in critically ill patients, including, oxygen desaturation (SaO₂<85%), variations in blood pressure of >20%, change in ventilatory support, muscle paralysis, position of the patient, administration of vasopressors (e.g. noradrenaline and vasopressin).
- Nurses' and medical staff's perception of the usability of both monitoring systems in daily routine

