4.3 Schedule of study procedure

With informed consent, the following routinely recorded clinical and laboratory data will be collected:

- Baseline demographics and comorbidities
- Administration of beta blockers or anti-arrhythmics
- Administration of sedative agents (general anaesthetics/opioids/benzodiazepines)
- Reasons for admission to ICU
- Daily biochemistry and haematology results
- Severity of illness scores, including APACHE II and daily SOFA scores
- Daily CAM ICU scores / delirium
- Daily cardiac rhythm as per nursing entry or clinical diagnosis
- Daily clinical parameters, including medications (vasopressors/ionotropes/steroids/muscle relaxants) and organ support
- Daily AKI stage, including treatment with RRT

After obtaining informed consent, continuous ECG data will be recorded using the two different devices. ECG data will then be processed to derive HRV using the methodology described by the European Society of Cardiology Taskforce guidelines.² Processing of ECG data entails checking

for and removal of extrasystole and ectopic beats with interpolation of QRS complexes as described elsewhere.² Continuous 24 hour ECG recording will then be divided into 5 minute epochs for which short term HRV values will be calculated. HRV will be calculated in the time domain, frequency domain and non-linear domains for each 5 minute epoch. Entire 24 hour ECG recordings will be used for long term HRV measures in the time domain, frequency domain and non-linear domains as described the Taskforce guidelines.² HRV data will then be analysed according to that described in the statistical methodology and analysis section. HRV data will be calculated by the Medical Engineering and Clinical Physics department at the Royal Liverpool and Broadgreen University Hospital. They will be blinded to any patient identifiable or clinical information.

Daily data will be collected until day 5 in ICU, day of discharge from ICU or day of death (depending on what occurs first). In addition, we will record ICU and hospital length of stay, ICU and hospital mortality and occurrence of arrhythmias during ICU stay, after 30 days, and after 90 days following enrollment. Data will be collected by accessing routinely available results in the patients' medical records, and if necessary, by contacting the patient's General Practitioner (GP).

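### The protocol names RR intervals as the Isansys input and ECG as the Holter input, yet describes ECG-level cleaning for both, so the counts of interpretable epochs may not be comparable

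*Protocol*

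**What the plan says.** **Primary outcome.** Section 2.1 gives "Number of interpretable monitoring epochs in each HRV monitoring system after elimination of artefacts, extra beats and interference". It does not say whether the elimination is done on the waveform or on the intervals.

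**Holter input.** Section 2.3: "ECG data will be downloaded from the holter device and analysis in holter device software package which derive HRV data". Section 6.2 adds that this software reports how many episodes are interpretable, together with ectopic beats and arrhythmias.

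**Isansys input.** Section 2.3: "RR interval data from the Isansys patch will be downloaded onto an Excel spreadsheet. The RR interval will be uploaded to Matlab". The synopsis (Statistical Methodology and Analysis) says the same. Neither place mentions export of the Isansys waveform.

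**Cleaning.** Section 2.3 goes on, without naming a device: "ECG data will undergo preprocessing to remove artefacts and ectopic beats". It then names the "Ornstein-Uhlenbeck third-order Gaussian process applied to the heart rate/RR interval". Section 4.3 says that "continuous ECG data will be recorded using the two different devices" and describes the processing as "removal of extrasystole and ectopic beats with interpolation of QRS complexes". Section 10.1 says that what goes to the analysing department is anonymised ECG data.

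**What the patch stores.** The device list in section 1 says that the patch samples filtered ECG at 1000 Hz and that "ECG data is transmitted and stored in a wireless interface called the Patient Gateway and Lifeguard Server".

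**The concern.** An RR spreadsheet holds a list of times between detected beats. It contains no QRS complexes and no signal, so the step in section 4.3 cannot be carried out on the Isansys input that section 2.3 and the synopsis name. If those two places are followed literally, Isansys epochs are judged in Matlab from intervals and Holter epochs are judged from ECG in vendor software.

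The primary outcome compares the two devices on exactly this judgement. Section 1 gives the open question as how each device copes with interference and artefact during physiotherapy, washing and repositioning. If the route to an interpretable epoch differs by device, a difference in counts, or the lack of one, cannot be attributed to the device. The Bland-Altman comparison of HRV measures has the same weakness, because the values being subtracted come from differently cleaned series.

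**Working it through.** The protocol gives no figure that bears on this point, so there is none to reproduce. The check sets the sections side by side and then illustrates what an interval-only filter can and cannot see.

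**1. The two routes as written**

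| Step | Isansys | Holter |
|---|---|---|
| Data downloaded | RR intervals (2.3, synopsis) | ECG (2.3) |
| Software | Excel, then in-house Matlab (2.3) | Vendor package (2.3, 6.2) |
| Source of the interpretable count | Not stated | Vendor software can report it (6.2) |
| Cleaning described in 4.3 | On ECG, with QRS interpolation | Same |
| Data sent for analysis per 10.1 | ECG | ECG |

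The first row and the last two rows do not agree for Isansys. With 5-minute epochs there are 24 × 60 / 5 = 288 per day, or 3 × 288 = 864 per patient over the 72-hour Holter recording. All of them pass through these routes.

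**2. Low-level timing error.** The assumptions here are not in the protocol: 400 beats per epoch, mean RR 750 ms, independent R-peak timing error with SD s on every beat, and a beat flagged if successive intervals differ by more than 20% (about 150 ms).

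A successive RR difference contains the error e(i+2) − 2e(i+1) + e(i), with variance (1 + 4 + 1)s² = 6s². Hence observed RMSSD = √(true RMSSD² + 6s²).

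| s (ms) | True RMSSD 10 ms | True RMSSD 20 ms |
|---|---|---|
| 3 | √(100 + 54) = 12.4 | √(400 + 54) = 21.3 |
| 5 | √(100 + 150) = 15.8 | √(400 + 150) = 23.5 |
| 10 | √(100 + 600) = 26.5 | √(400 + 600) = 31.6 |
| 20 | √(100 + 2400) = 50.0 | √(400 + 2400) = 52.9 |

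Simulation of 500 epochs per setting reproduces these values. The share of beats flagged is 0% up to s = 10 ms. At s = 20 ms it is about 0.4% (true RMSSD 10 ms) and 0.6% (true RMSSD 20 ms). No simulated epoch would be rejected by a rule of more than 5% flagged beats.

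**3. Gross noise.** A second simulation used mean RR 700 ms, SDNN about 20 ms, 430 beats, a flag at more than 20% from the local median, and rejection above 5% flagged. All epochs with 10% or 20% spurious or missed beats were rejected. None were rejected at 2%, where SDNN before removal of flagged beats rose from about 20 ms to 75 ms (spurious) or 97 ms (missed). At 2%, however, 3.2% and 1.9% of intervals were flagged, so most of those beats could still be removed within a retained epoch. Noise of SD 30 ms on up to 20% of intervals led to no rejections, and SDNN rose only to about 24 ms.

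**4. The opposite error.** Appendix 1 lists a normal SD1 of 57.01 ms, which implies an RMSSD of √2 × 57.01 = 80.6 ms. At that level an error SD of 20 ms gives √(6500 + 2400) = 94.3 ms, only 1.17 times too high. With no noise at all, 150 / 80.6 = 1.86, so under a normal distribution about 6% of genuine beats exceed the 20% limit, and the 5% rule would reject a clean epoch.

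**The case against.** The strongest reply is that the text does not settle on RR intervals alone. It says RR data will be downloaded, not that nothing else will be. Section 10.1 says ECG data are sent for analysis, and sections 2.3 and 4.3 speak of preprocessing the ECG. This stands: the documents show an inconsistency, not a firm decision to leave the waveform behind.

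Interval-level cleaning is also part of the stated method. The Gaussian process works on the heart rate or RR series, and section 1 mentions techniques such as the Poincaré plot for automatic artefact removal. So it would be wrong to say that artefacts cannot be removed from Isansys data. Neither technique, however, supplies the QRS-level step of section 4.3. The illustration above does not model the Gaussian process.

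A reader might infer three stronger things that the protocol does not support:

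- That waveform cleaning defines an interpretable epoch. Section 2.1 contains no such definition, and an operational rule may sit in an analysis plan that is not shown.
- That noisy Isansys epochs will be counted and the comparison will favour the patch. Gross noise is caught, a filter can also reject true variability, and nothing shows that the vendor software would reject epochs with small timing errors.
- That RMSSD will be five times too high. That needs an assumed independent error of SD 20 ms on every beat with a true RMSSD of 10 ms. At 3 ms the factor is about 1.2.

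Finally, this is a pilot, and defining amendments to data capture is one of its secondary objectives. That lowers the stakes but does not remove the problem, because two differently processed counts would not show which amendment is needed.

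**Conclusion.** The point holds in a limited form. Section 2.3 and the synopsis name RR intervals as the Isansys input, while sections 2.3, 4.3 and 10.1 describe ECG being sent and cleaned, in 4.3 for both devices with QRS interpolation. These statements cannot all be followed. Followed as section 2.3 is written, the primary count and the HRV agreement analysis compare device plus processing route, not device alone.

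Neither the size nor the direction of any bias can be derived from the documents. Under the stated assumptions, subtle timing error can inflate RMSSD by a factor of about 1.2 to 5 at a true RMSSD of 10 ms, and by about 1.1 to 2.6 at 20 ms, with under 1% of beats flagged. At the higher variability implied by Appendix 1 the inflation is small and over-rejection becomes possible. All of this depends on filter and rejection thresholds that the protocol does not state. The point should be resolved before data collection, but it does not make the study unworkable.

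**What to change.** Reconcile the synopsis with sections 2.3, 4.3 and 10.1 so that they name the same input and the same cleaning route for each device. Suggested content for section 2.3 and the synopsis:

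- The stored Isansys ECG and the Holter ECG are both exported with device time stamps.
- The same R-peak detection, beat classification and signal-quality rule is applied to both waveforms before RR intervals are formed and interpretable epochs are counted.
- Where the Isansys waveform cannot be exported, the RR series of both devices for those periods go through the same Matlab cleaning and the same interpretability rule, and these periods are reported separately. They are not scored as uninterpretable, since that would penalise the patch for an export limit rather than for signal quality.

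**Cost.** Extra export, storage and processing work, with no change for patients. Section 1 says the ECG is sampled at 1000 Hz and stored, but not that the full waveform is kept or can be exported. That must be confirmed before data collection.

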SAE	Serious Adverse Event
SDV	Source Document Verification
SOP	Standard Operating Procedure
TSC	Trial Steering Committee

1. Introduction

The healthy cardiovascular system is in a state of dynamic stability.¹ This stability is achieved by altering heart rate, blood pressure and other factors to react to internal and external stressors.¹ Alterations in heart rate and blood pressure is under the control of the autonomic nervous system. HRV analysis is a method used to assess cardiac autonomic function.² Heart rate variability analysis assesses the variability between heart beats which reflect alterations in heart rate due to fluctuations in the autonomic nervous system.³ HRV is therefore considered a measure of neurocardiac function that reflects heart-brain interactions.⁴

Autonomic dysfunction is often seen in critically ill patients' and as part of disorders requiring admission to the intensive care unit.⁵ Assessment of the autonomic nervous system may provide information regarding pathophysiology, severity and prognosis associated with these disorders.⁵ Depressed HRV has been associated with increased 30-day all-cause mortality in intensive care unit patients.⁶ Furthermore alterations in heart rate variability have been recognised in sepsis, multiorgan dysfunction syndrome, acute ischaemic stroke, traumatic brain injury, Guillain-Barre syndrome and following myocardial infarctions and malignant arrhythmias.⁵

HRV analysis has seen a significant increase in clinical use since the 1960's. However the significance and meaning of many different HRV measures has led to the potential for incorrect conclusions and interpretations.² In 1996 the European Society of Cardiology and the North American Society of Pacing and Electrophysiology published guidelines for the Standard of measurement, physiological interpretation, and clinical use of heart rate variability.² The goal of these guidelines was to, 'standardise nomenclature and develop definitions of terms; specify standard methods of measurement; define physiological and pathophysiological correlates; describe currently appropriate clinical applications and identify areas for future research.'² These guidelines continue to form the basis and define the conduct of much of the research into HRV.

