Appendix 1: Analysis of HRV variables

Parameter	Units	Description	Normal range
SDNN	ms	Standard deviation of the NN intervals	101.19
SDANN	ms	Standard deviation of average NN intervals	41.47
pNN50	%	Percentage of successive RR intervals that differ by more than 50ms	18.80
RMSSD	ms	Root mean square of successive RR interval differences	0.08
LF power	ms ²	Absolute power of the low frequency band (0.04 – 0.15Hz)	2534.91
HF power	ms ²	Absolute power of the high frequency band (0.15 – 0.4Hz)	2592.32
VLF power	ms ²	Absolute power of the very low frequency band (0.033 – 0.04Hz)	8307.38
LF/HF ratio	%	Ration of LF to HF power	128.78
SD1	ms	Poincre plot standard deviation perpendicular to the line of identity	57.01
SD2	ms	Poincre plot standard deviation along the line of identity	134.13
SD1/SD2 ratio	%	Ratio of SD1 to SD2	2.49

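### Interchangeability is judged on limits of agreement from untransformed differences for every HRV measure, and the check for error that grows with level is optional and has no consequence

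*Protocol*

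**What the plan says.** Protocol section 2.3 compares the devices by Bland-Altman analysis: "The difference between measures recorded from the Holter monitor and the Isansys wireless monitor will be plotted against the average value for each HRV measure". No log, ratio or percentage scale is named. The next sentence adds: "Any measure of relationship between the measurement error and the estimate of the true value (average of the two measurements) can be examined". It does not say what happens if a relationship is found.

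The decision rule comes after this. It ties a pass to the 95% limits of agreement and to the absence of problems in clinical reading. When that condition is met, the stated consequence reads: "then the Isansys wireless device can be considered to be interchangeable with the gold-standard holter monitoring device". The synopsis repeats this rule.

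The measures are broad: "We will use time domain measures, frequency domain measures and non-linear measures such as the poincare plot, approximate and sample entropy". Appendix 1 lists the three spectral bands in ms², for example "Absolute power of the low frequency band", beside SDNN, SDANN, RMSSD, pNN50, SD1, SD2 and two ratios. Normalised units appear in the introduction as background only.

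**The concern.** One pair of limits, mean difference ± 1.96 SD, describes agreement well only if the size of the error does not depend on the level of the measure. Spectral power is a positive, squared quantity, usually right-skewed across patients, so a proportional error is plausible. In that case a few patients with high power supply most of the variance of the differences. The band they produce is loose where HRV is low and tight where HRV is high.

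The low end matters to this protocol. Its introduction states: "Depressed HRV has been associated with increased 30-day all-cause mortality in intensive care unit patients". The study is also meant to guide which device is used in later HRV research. A statement of interchangeability that is least discriminating in patients with low HRV would be a weak basis for that choice.

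**Working it through.** The protocol gives no device error, between-patient spread, level for depressed HRV or acceptable difference. There is therefore no stated figure to reproduce, and every size below is conditional.

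**Inputs**
- n = 30 (synopsis and section 4.5). Section 3.1 says 40, which gives nearly the same results.
- Level T log-normal with median 100 ms² and log-SD s = 0.5 to 1.5 (assumption). The median cancels from all shares and ratios.
- Proportional error, with SD of ln(Isansys/Holter) e = 0.10 to 0.20 (assumption).
- 4,000 simulated studies per setting. Repeat runs agree within about one percentage point on the shares.

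**Step 1: width of the raw limits.** With proportional error, SD of the difference ≈ e × 100 × exp(s²). For s = 0.5 and e = 0.10, the half-width is 1.96 × 0.10 × 100 × 1.284 = 25.2 ms². For larger s this formula overstates the width usually seen with 30 patients, so simulated medians are used. At e = 0.20 they are 48, 65, 83 and 172 ms² for s = 0.5, 0.8, 1.0 and 1.5.

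**Step 2: who sets the limits** (e = 0.15). If all patients contributed equally, the 8 highest of 30 would supply 8/30 = 27% of the sum of squared differences.

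| s | Share from 8 highest | Coverage, 8 lowest | Coverage, 8 highest |
|---|---|---|---|
| 0.5 | 60% | 99.9% | 82% |
| 0.8 | 75% | 100% | 78% |
| 1.0 | 83% | 100% | 77% |

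Overall coverage stays at 93% to 95%, so the imbalance is hidden in the total. With a narrow spread (s = 0.3) it is milder: 47%, 99.4% and 87%.

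**Step 3: share of patients for whom a given reading would lie inside.** With U the upper limit, a 1.5-fold reading is inside when 0.5 × T ≤ U, that is T ≤ 2U. For s = 0.5 and e = 0.10, 2U = 50.4 and the share is Φ(ln(0.504)/0.5) = Φ(−1.37) ≈ 9%. Simulated shares:

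| s | 1.5-fold, e = 0.10 | 1.5-fold, e = 0.20 | 2-fold, e = 0.20 |
|---|---|---|---|
| 0.5 | 9% | 47% | 9–10% |
| 0.8 | 31% | 62% | 31% |
| 1.0 | 43% | 68% | 43% |
| 1.5 | 64% | 78–79% | 63–64% |

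**Step 4: the same result as a ratio.** The largest ratio inside the limits at level t is 1 + U/t. At the 10th percentile of HRV with e = 0.10 it is 1.45, 1.90 and 2.48 for s = 0.5, 0.8 and 1.0. On the log scale the limit is the same at every level: exp(1.96 × 0.10) = 1.22.

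**Step 5: contrast with additive error.** If the error SD is constant at 10 ms² (10% of the median), high-HRV patients do not set the limits. The half-width is 1.96 × 10 = 19.6 ms². At s = 0.8 the 10th percentile of T is 100 × exp(−1.28 × 0.8) = 35.9, so the ratio is 1 + 19.6/35.9 ≈ 1.55 (simulated 1.54). A constant limit is still a larger ratio at low HRV, but it now describes the error correctly.

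**Step 6: does the log scale repair the rule?** No. If the 8 lowest-HRV patients of 30 truly carry a 2-fold error, the upper log limit widens to 2.2 to 2.5, and 87% to 99% of those patients still fall inside it.

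**The case against.** **The scale is a matter for the SAP.** The protocol does not exclude a transformation, and it foresees looking at error against level. To say that the rule would stay on the raw scale even after a relationship was found is an inference from silence. That stands. But the protocol does specify a plain difference for each measure and attaches a decision to it, so this is a stated method with an open end and not merely an omitted detail.

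**The fold-errors are not the protocol's.** A reader might infer that 1.5-fold to 2-fold device errors will pass in patients with depressed HRV. The documents do not support this. They give none of the figures needed, and the share for 1.5-fold falls to 9% at the mild end of the assumptions. The shares in step 3 also ask where a hypothetical reading would fall within limits built from a better device. A device that really made such errors would produce different limits.

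**Logs can be overstated too.** At e = 0.20 the population log limit is exp(1.96 × 0.20) = 1.48, just under 1.5, but the estimated limit exceeds 1.5 in about 39% of studies of 30 patients. At e = 0.30 it does so in 97%, and a 1.5-fold reading is then inside for every patient, against 76% to 85% of patients on the raw scale. So log limits would not reliably exclude a 1.5-fold reading.

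**Proportional error is undocumented.** The introduction speaks of interference and artefacts, which need not scale with HRV. With additive error (SD 10 ms², s = 0.8), raw limits are about ±19 ms², while log limits would allow about 100 ms² in the 8 highest patients. This stands, and it rules out imposing logs without a check.

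**Stakes.** This is a pilot, and agreement on HRV measures is a secondary outcome. That limits the severity.

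**Conclusion.** The point holds in a conditional form. The protocol bases the interchangeability decision on limits from untransformed differences for every HRV measure, including LF, HF and VLF power, and its check on level-dependent error is optional and without consequence. If error is roughly proportional to level and log-SD is 0.5 or more, the raw limits cover about 100% of the 8 lowest-HRV patients and 77% to 82% of the 8 highest. The 9% to 79% range for a 1.5-fold reading rests on 10% to 20% error and log-SD 0.5 to 1.5. It shows how far the result depends on unknowns and does not forecast what this device will do.

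Two stronger readings are not supported: that errors of a particular size will pass, and that a log scale alone would stop them. The limits come from the same data that they judge, and no acceptable difference is set, so about 95% of differences fall inside on either scale. The change should be made, but the point does not affect the primary outcome, the number of interpretable epochs.

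**What to change.** In section 2.3 and the synopsis:

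1. Make the check of error against level mandatory for each HRV measure, and state what follows from it.
2. For positive, right-skewed measures (LF, HF and VLF power, and SDNN, SDANN, RMSSD, SD1, SD2 and the two ratios where error grows with level), do the Bland-Altman analysis on log values. Report the geometric mean Isansys/Holter ratio with ratio limits of agreement.
3. For pNN50, and any measure where error still varies with level, use regression-based limits.
4. Keep raw differences where error is constant.
5. For each measure used to claim interchangeability, fix an acceptable ratio or difference in advance and compare the limits with it. Without this, changing the scale does not repair the rule.

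The cost is protocol or SAP wording, a few lines of code, and the investigators' agreement on the acceptable values. No new patients or data are needed. The small downside is that the log-scale measures are reported as ratios and not in ms or ms².
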